7 STUDY RATIONALE AND PURPOSE

Since the introduction of imatinib and subsequent second generation tyrosine kinase inhibitors (2GKIs), the prognosis of chronic-phase Chronic Myeloid Leukemia (CP-CML) has improved greatly. Initially considered to be a lethal disease with a median estimated overall survival (OS) of 3.2 years, CP-CML is now regarded as a chronic disease with a life expectancy similar to that of the healthy population. However, CML patients, despite their treatment response, cannot be considered cured and should take the treatment indefinitely.

Recently, data from different clinical trials have shown how a minority of patients who achieve a deep molecular response with imatinib and maintain the response, could stop treatment safely. Therefore, treatment free remission (TFR) has been established as a new goal for CML patients. However, currently, TFR is only available for a small group of patients since deep molecular response is achieved by 5 years only in approximately 20% of patients treated with imatinib, and unfortunately, 50% of patients will eventually relapse. In addition, recent data have shown a time exposure to imatinib longer than 7 years as a prognostic factor for TFR.

Starting treatment with 2GTKIS (dasatinib, nilotinib and bosutinib) have demonstrated higher probabilities of deep molecular responses.

Suppression of the immune system in CML patients at diagnosis is mediated in part by hematopoietic stem cells, which acquire a proliferative/survival advantage and lose the ability to undergo apoptosis. Release of tumor-derived cytokines/chemokines drives the expansion of immune suppressor MDSC and Treg, facilitating downregulation of antitumor effector immunity. PD-L1 is upregulated on CML cells, where it interacts with the co-inhibitory receptor PD-1, and contributes to protection of the malignant cells from immune destruction. MDSC originate from the malignant BCR-ABL1 clone and mediate their suppressive activity via a number of mechanisms, including increased production of reactive oxygen and nitrogen species (NO, ROS), arginase-1, and TGF- β 1. MDSC can induce Treg expansion, and Treg also express PD-1 to promote enhanced suppressor function. We know how PD-1 is expressed at diagnosis in CML patients on T cells, and that its expression considerable decreases after achieving deep molecular response. The combination of TKI plus interferon has translated into higher probabilities of deep molecular responses compared to TKI monotherapy in several clinical trials.

It is also known how the immune system plays a crucial role in treatment free remission strategies. The lack of overt relapse in patients who have previously achieved a deep molecular response, despite the presence of very low levels of residual disease has been attributed to immunological control of CML. IFN/imatinib induction treatment followed by a temporary IFN maintenance may enable a higher rate of treatment discontinuation in CML patients in at least MMR when stopping. The TIGER study (NCT01657604) is currently investigating de-escalating maintenance therapy using low dose IFN as an inducer of immune surveillance following nilotinib discontinuation.

Upregulation of the immune checkpoint receptor PD-L1 and its receptors, PD-1 and B7.1, has been demonstrated in peripheral blood mononuclear cells from patients with CML.

During the past 5 years, immune checkpoint inhibitors have revolutionized the management and treatment of cancer, because they have been associated with striking improvements in clinical outcomes in patients with some tumor types.

Programmed Death Ligand 1 (PD-L1) is an immune-checkpoint protein expressed on tumor cells and tumor-infiltrating immune cells that downregulates antitumoral T-cell function through binding to programmed death 1 (PD-1) and B7.1 (also known as CD80) receptors. The engineered, humanized IgG1 monoclonal anti-PD-L1 antibody atezolizumab blocks PD-L1–PD-1 and PD-L1–B7.1 interactions, resulting in restoration of antitumor T-cell activity and enhanced T-cell priming. Blocking PD-L1–B7.1 binding on T cells and antigen-presenting cells might additionally inhibit downregulation of immune responses, thus preventing inhibition of T-cell activation and cytokine production. Direct targeting of PD-L1 leaves the PD-L2–PD-1 interaction intact, potentially avoiding effects on immune homoeostasis. Atezolizumab is engineered to eliminate binding to Fc receptors and to prevent Fc-effector function. This

modification eliminates antibody-dependent cell mediated cytotoxicity and thus avoids potential loss of PD-L1-expressing T-effector cells and reduced anticancer immunity.

The combination of bosutinib plus atezolizumab in first line CML chronic phase patients would increase molecular responses and therefore TFR probabilities in newly diagnosed CML patients.

8 STUDY OBJECTIVE

8.1 Primary Objective

The primary objective is to evaluate the safety profile of bosutinib 400mg/day in combination with atezolizumab as a first line treatment in participants with chronic phase-chronic myeloid leukemia.

8.2 Secondary Objectives

- To evaluate the Major Molecular Response (MMR) and Molecular Response (MR) rates at 3, 6, 12 months and at the End of Treatment (EoT) visit. Based on:
 - MMR is defined as \geq 3-log reduction in BCR-ABL transcripts or a ratio of $\leq 0.1\%$ on the International Scale (IS)
 - Molecular Response (MR): As defined in section 4. Definition of Terms
- Percentage of participants alive at months 6 and 12 and at the EoT visit.
- Number of confirmed MR4 and MR4.5 at end of treatment.
- The rate of confirmed MR4 and MR4.5 at the end of treatment.
- Number of Complete Cytogenetic Responses (CCyR) at 1 year]
- The rate of Complete Cytogenetic Response (CCyR) at 1 year.
- Number of days to response (CCyR, MMR, MR4, MR4.5). [Time Frame: at the EoT visit]
- The median time to response and the overall estimated probability of response (CCyR, MMR, MR4, MR4.5).
- Number of overall surviving patients [Time Frame: at the EoT visit]
- Number of progression-free survival patients.[Time Frame: at the EoT visit]
- Number of failure-free survival patients. [Time Frame at the EoT visit]
- Number of event-free survival patients. [Time Frame: at the EoT visit]
- Immunological Studies

9 STUDY DESIGN

This is a phase Ib/II, two arms, open-label and dose-escalation study designed to determine the safety profile and the recommended phase III dose (RP3D) of bosutinib when administered in combination with atezolizumab in naïve patients with chronic myeloid leukemia in chronic phase. This study has two groups of patients (Figure 1).

[figure not shown]
[figure not shown]
[figure not shown]

Figure 1. Chronogram of the study

LAST 26 PATIENTS INCLUDED

9.1 Patient Screening

This study will be conducted on those naïve patients with chronic-phase Chronic Myeloid Leukemia (CP-CML) who meet the established selection criteria (see below). The patients that sign the IC and meet the selection criteria will be selected to enter the study.

Results of all screening evaluations must be reviewed by the Principal Investigator or his/her designee prior to the enrollment of a patient into the study to assure that all inclusion and none exclusion criteria have been satisfied.

All study patients must be thoroughly informed about all aspects of the study, including the study visit schedule and required assessments for informed consent. The written informed consent must be obtained prior to any screening evaluations. If a patient is unable to read, an impartial witness should be present during the entire informed consent discussion.

This is an open label clinical trial, and no randomization or blinding procedures are required.

The patients will be divided in two groups, with different start points, and will have three different therapy combinations during the study, which are described below. The first 10 patients included in the study will begin first. If at least 9 of these patients do not suffer DLTs during the first 2 cycles of the combined treatment (bosutinib 400 mg/day plus atezolizumab 840 mg every two weeks), the following 26 patients will be included, otherwise, the study will be terminated.

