Study Objectives	
Primary endpoint: Safety profile of bosutinib 400 mg daily in combination with atezolizumab in participants with chronic myeloid leukemia as first line treatments
 
Secondary endpoints:
 
• To evaluate the Major Molecular Response (MMR) and Molecular Response (MR) rates at 3, 6, 12 months and at the End of Treatment (EoT) visit.• Percentage of Participants Alive at Month 6, 12 and the EoT visit.• Number of confirmed MR4 and MR4.5 at end of treatment.• The rate of confirmed MR4 and MR4.5 at the end of treatment.• Number of Complete Cytogenetic Responses (CCyR) [Time Frame: At 1 year]• The rate of Complete Cytogenetic Response (CCyR) at 1 year.• Number of days to response (CCyR, MMR, MR4, MR4.5) [Time Frame: at the EoT visit]• The median time to response and the overall estimated probability of response (CCyR, MMR, MR4, MR4.5).• Number of overall surviving patients [Time Frame: at the EoT visit]• Number of progression-free survival patients [Time Frame: at the EoT visit]• Number of failure-free survival patients [Time Frame at the EoT visit]• Number of event-free survival patients [Time Frame: at the EoT visit]• Immunological Studies
Study Design	
This is a phase Ib/II, simple arm, open-label and dose-escalation study designed to determine the safety profile and the recommended phase III dose (RP3D) of bosutinib when administered in combination with atezolizumab in naïve patients with chronic myeloid leukemia in chronic phase.
 
The patients will be divided in two groups, with different start points, and will have three different therapy combinations during the study, which are described below. The first 10 patients included in the study will begin first. If at least 9 of these patients do not suffer DLTs during the first 2 cycles of the combined treatment (bosutinib 400 mg/day plus atezolizumab 840 mg every two weeks), the following 26 patients will be included, otherwise, the study will be terminated.

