	
– First therapy
 
All patients included, both the first 10 patients and the next 26 patients, will receive bosutinib 400 mg/day in monotherapy for one cycle. All patients who tolerate this cycle of bosutinib treatment will continue to the second therapy (bosutinib plus atezolizumab).
 
– Second Therapy
 
*Group 1: The first 10 patients included
 
Only for the first ten patients included in the study, atezolizumab will be introduced at a dose of 840 mg every two weeks combined with 400 mg/day of bosutinib for 2 cycles (8 weeks). These patients will be closely monitored for safety issues.
 
If dose-limiting toxicities (DLTs) appear in 2 or more patients the study will end. If no relevant safety issues regarding the combination of drugs is detected the study will continue.
 
These initial 10 patients will cross-over from bosutinib 400 mg/day plus atezolizumab 840 mg every 2 weeks to bosutinib 400 mg/day plus atezolizumab 1680 mg every 4 weeks for 10 cycles (40 weeks).
 
*Group 2: The next 26 patients included
 
After receiving bosutinib 400 mg/day in monotherapy for one cycle (1st therapy), the last 26 patients included will receive bosutinib 400 mg/day plus atezolizumab 1680 mg every 4 weeks for 12 cycles.
 
Patients will be closely monitoring. If DLTs appear in 2 or more patients at a dose of 1680 mg of Atezolizumab every 4 weeks, the dose of atezolizumab will be reduced for all patients to an 840 mg Atezolizumab every 2 weeks dose.
 
All patients completing 12 treatment cycles (48 weeks) will begin the last therapy of study.
 
– Third Therapy
 
All patients completing cycle 12 with the combined bosutinib plus atezolizumab therapy will continue with bosutinib 400 mg/day in monotherapy for 12 more cycles.
 
A DLT would include either of the following adverse events occurring during of the bosutinib/atezolizumab therapy and that is considered at least possibly related to bosutinib and/or atezolizumab:
 
• Grade 4 neutropenia (<500/μl) persisting for >7 day duration or Grade 4 white cell count decrease for >7 day duration (<1000/μl).• Febrile neutropenia (ANC<1000/μl and fever \geq38.5°C).• Grade 4 thrombocytopenia >48 hour duration or with bleeding requiring platelet transfusion.• Any Grade 3 or 4 clinically evident non-hematological toxicity• Any \geqGrade 3 toxicity that requires >14 days to resolve (to \leqGrade 1 despite optimal medical therapy). 
DTLs will be graded according to the NCI CTCAE, v5.0.

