9.2 First therapy

All patients included, both the first 10 patients and the next 26 patients, will receive bosutinib 400 mg/day in monotherapy during one cycle of treatment. All patients who tolerate this cycle of bosutinib treatment will continue to the second therapy (bosutinib plus atezolizumab).

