9.3 Second Therapy

9.3.1 Group 1: The first 10 patients

Only for the first ten patients included in the study, atezolizumab will be introduced at a dose of 840 mg every two weeks combined with 400 mg/day of bosutinib for 2 cycles (8 weeks). These patients will be closely monitored for safety issues.

If dose-limiting toxicities (DLTs) appear in 2 or more patients the study will end.

A DLT would include either of the following adverse events that occurred during bosutinib therapy in combination with atezolizumab, if it is considered at least possibly related to bosutinib and/or atezolizumab:

- Grade 4 neutropenia (<500/ μ l) persisting for > 7 day duration or Grade 4 white cell count decrease for >7 day duration (<1000/ μ l).
- Febrile neutropenia (ANC<1000/ μ l and fever \geq 38.5°C).

- Grade 4 thrombocytopenia > 48 hour duration or with bleeding requiring platelet transfusion.
- Any Grade 3 or 4 clinically evident non-hematological toxicity.
- Any ≥Grade 3 toxicity that requires >14 days to resolve (to ≤Grade 1 despite optimal medical therapy).

DLTs will be graded according to the NCI CTCAE, v5.0.

If no relevant safety issue, regarding the combination is detected the study will continue.

These initial 10 patients will cross-over from bosutinib 400 mg/day plus atezolizumab 840 mg every 2 weeks to bosutinib 400 mg/day plus atezolizumab 1680 mg every 4 weeks for 10 cycles (40 weeks).

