9.3.2 Group 2: The next 26 patients

After receiving bosutinib 400 mg/day in monotherapy for one cycle (1st therapy), the last 26 patients included will receive bosutinib 400 mg/day plus atezolizumab 1680 mg every 4 weeks for 12 cycles.

Patients will continue to be closely monitoring. If DLTs appear in 2 or more patients at a dose of 1680 mg of Atezolizumab every 4 weeks, the dose of atezolizumab will be reduced for all patients to an 840 mg Atezolizumab every 2 weeks dose.

All patients completing 12 treatment cycles (48 weeks) will begin the last therapy of study.

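### The Group 1 go/no-go decision counts the first 10 patients included, not 10 patients evaluable for DLT, so the stated minimum of 10 for DLT evaluation is not secured

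*Protocol*

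**What the plan says.** **Who is counted.** The Synopsis (Study Design) and Protocol 9.1 define Group 1 by inclusion: "The first 10 patients included in the study will begin first". The next 26 are enrolled "If at least 9 of these patients do not suffer DLTs during the first 2 cycles of the combined treatment"; otherwise the study is terminated.

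**When exposure begins.** Under Protocol 9.2 every included patient first takes bosutinib alone for one cycle, and only those who tolerate it move to the combination. Protocol 9.3.1 and SAP 4.1 confine DLTs to the combination: "A DLT would include either of the following adverse events that occurred during bosutinib therapy in combination with atezolizumab".

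**The second rule.** Protocol 9.3.1, the Synopsis (Second Therapy) and SAP 4.1 give a stop trigger with no denominator: "If dose-limiting toxicities (DLTs) appear in 2 or more patients the study will end". Continuation is worded separately: "If no relevant safety issue, regarding the combination is detected the study will continue". The SAP carries the 2-or-more rule but not the 9-of-10 rule.

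**Planned numbers.** The Synopsis (Statistical Analysis), Protocol 15.5 and SAP 4.3 set a minimum of 10 patients for DLT evaluation if no DLT is observed. They also assume that at most 15% of those included will not go on to the combination because of side effects, so that 30-31 of 36 receive it.

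The visible text has no definition of a DLT-evaluable patient, no replacement rule for Group 1 and no instruction for counting a patient who never starts the combination. The design figures in Protocol section 9 and SAP 4.1 are not available to this review.

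**The concern.** The plan budgets for losses before the combination across the whole trial, but makes no provision for them in the cohort that decides whether the trial goes on. A single non-starter among the first 10 leaves fewer exposed patients than the stated minimum, and the rules as written can still open Group 2. The primary objective is safety and the decision exposes up to 26 more patients, so the amount of evidence behind it matters.

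The missing denominator also leaves open what the 9 are counted out of. A patient who never receives atezolizumab has not suffered a DLT, but is no evidence that the combination is tolerable. The documents do not say how such a patient scores.

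**Working it through.** **Inputs.** 36 patients, at most 15% not starting, 30-31 treated, minimum 10 for DLT evaluation (Protocol 15.5, SAP 4.3); 9-of-10 rule (Protocol 9.1); 2-or-more rule (Protocol 9.3.1, SAP 4.1). The plan gives no expected loss and no unacceptable DLT rate. Losses *q* of 5, 10 and 15% (15% being the plan's ceiling), independence between patients, and DLT rates *p* of 0, 10 and 30% are therefore assumptions.

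**1. The plan's own figure.** 36 × (1 − 0.15) = 30.6, which matches 30-31. The allowance is thus taken over all 36, Group 1 included.

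**2. Chance that all 10 start.** Let S be the number starting, S ~ Bin(10, 1 − *q*). P(S = 10) = (1 − *q*)^10, so 0.95^10 = 59.9%, 0.90^10 = 34.9% and 0.85^10 = 19.7%. At an assumed 2% loss, 0.98^10 = 81.7%.

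**3. Non-starters counted as DLT-free (the literal reading).** At least 9 of 10 without a DLT is then the same event as fewer than 2 DLTs, so the two rules agree. Among the 10 included, DLTs follow D ~ Bin(10, x) with x = (1 − *q*)*p*, and P(D ≤ 1) = (1 − x)^10 + 10x(1 − x)^9. For *p* = 0.30:

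| Loss | x | P(fewer than 2 DLTs) |
|---|---|---|
| 0% | 0.300 | 14.9% |
| 5% | 0.285 | 17.4% |
| 10% | 0.270 | 20.2% |
| 15% | 0.255 | 23.3% |

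The rise is 2.5, 5.3 or 8.4 percentage points.

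**4. What zero DLTs would show.** The exact two-sided 95% upper bound for 0 of n is 1 − 0.025^(1/n): 30.8% for n = 10, 33.6% for n = 9 and 36.9% for n = 8.

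**5. Only exposed, DLT-free patients counted toward the 9.** With 8 or fewer starters the 9 cannot be reached even with no DLT, so Protocol 9.1 terminates while the 2-or-more trigger is not met. The chance of this with zero DLTs is the sum over s ≤ 8 of C(10, s)(1 − *q*)^s *q*^(10−s) (1 − *p*)^s.

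| Case | 5% loss | 10% loss | 15% loss |
|---|---|---|---|
| 0 DLTs, S ≤ 8, *p* = 0 | 8.6% | 26.4% | 45.6% |
| 0 DLTs, S ≤ 8, *p* = 10% | 3.8% | 11.8% | 20.8% |
| Exactly 1 DLT, S ≤ 9, *p* = 10% | 15.5% | 25.0% | 30.6% |

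In the last row Protocol 9.1 again terminates and the trigger is again not met, but no section requires the study to continue. It is shown separately for that reason.

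**Limits.** The figures describe the DLT count alone, because the condition of no relevant safety issue has no stated criterion. They cover non-starters only. Patients who leave during the 8-week window, which Protocol 9.5 permits for adverse events or toxicity, would add to the shortfall; the documents give no figure for them.

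**The case against.** **Ten treated patients may be what was meant.** Protocol 9.3.1 speaks of introducing atezolizumab in the first ten and of these initial ten crossing over, and the minimum of 10 is itself a stated requirement. On that reading the two rules coincide and only the replacement mechanics are unwritten. This is a fair account of the likely intention. It does not remove the gap, since no rule delivers the ten.

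**The loss may be small.** 15% is a ceiling, and dose reduction (11.6.1) or an interruption of up to one month (11.6) may keep some patients in. That stands. At a 2% loss the shortfall occurs in 18.3% of cases (100 − 81.7).

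**The effect is modest and other safeguards exist.** Under the literal reading the shift is 2.5 to 8.4 points in an exploratory study without a formal sample size. Continuation also requires no relevant safety issue, Group 2 has its own rule ("If DLTs appear in 2 or more patients at a dose of 1680 mg of Atezolizumab every 4 weeks") and the sponsor may terminate for safety (18.7). These limit the consequence. But the first has no criterion, the second acts only once patients are receiving the 1680 mg schedule, and none supplies the denominator.

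**A stronger reading is tempting.** A reader might infer that the two rules contradict each other outright, so that one non-starter plus one DLT would oblige the study both to end and to continue. The documents do not support that. Protocol 9.3.1 and SAP 4.1 give a condition sufficient to stop; they do not say that 0 or 1 DLT means continue. A single DLT may itself be a relevant safety issue, and a stop trigger can coexist with a stricter condition for going on. Adding the one-DLT cases to the clash, which would give 19.3, 36.8 and 51.4% at a 10% DLT rate, would overstate it.

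**Conclusion.** The concern holds as a gap in the decision rule and should be fixed. The minimum of 10 for DLT evaluation is stated but not secured: at assumed independent losses of 5, 10 and 15%, the first 10 included yield 10 exposed patients with probability 59.9, 34.9 and 19.7%. If non-starters count as DLT-free, the two rules agree but the decision is somewhat more lenient and rests on less evidence.

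A clear textual clash arises only if exposed patients alone count toward the 9, there are no DLTs, 8 or fewer start, and no other relevant safety issue is detected. The documents do not settle whether that reading applies. Confidence is high for the unsecured minimum and moderate for the rule conflict. All probabilities depend on the assumed losses, independence and, where used, the illustrative DLT rates.

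**What to change.** Reconcile the Synopsis (Study Design, Second Therapy and Statistical Analysis), Protocol 9.1, 9.3.1 and 15.5, and SAP 4.1 and 4.3. The existing threshold, unchanged, should be stated once in both documents with 10 DLT-evaluable patients as its denominator. Non-evaluable patients should be replaced from within the 36.

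The sponsor should define evaluable, including the minimum exposure in the two-cycle window. That window holds four infusions, while Protocol 11.6 lets a patient stay on study with up to three missed administrations, so being on study does not by itself show adequate exposure. The sponsor should also state how patients who leave the window because of toxicity short of a DLT are counted and reported, so that replacement does not selectively remove poor tolerators.

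**Cost.** Reaching 10 starters takes on average 10/(1 − *q*) = 10.5, 11.1 or 11.8 inclusions at 5, 10 or 15% loss, so Group 2 loses about 0.5, 1.1 or 1.8 of its 26. For at least 95% assurance of 10 starters, allow 12, 13 or 14 inclusions (98.0, 96.6 and 95.3%). Each replacement can delay the opening of Group 2 by up to 12 weeks from its first dose (4 weeks of bosutinib alone plus the 8-week window). The 10/26 split and the headings of Tables 14-17 need consequential edits.
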